
Subjects willing to discontinue AChEI and/or memantine in order to take part in the study must be documented to be eligible according to clinical inclusion / exclusion criteria, screening MRI and amyloid positive PET scan, before these drugs are discontinued.

Only subjects with a CDR 0.5 will undergo F-FDG-PET. F-DG-PET images are to be obtained prior to Visit 2 (and at least 60 days after the last dose of AChEI and/or memantine) for purposes of establishing the baseline assessment. Completion of this scan must be confirmed prior to randomization; other than confirmation of acceptable quality, the results per se are not considered for eligibility at the Screening visit. The baseline

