## **11 SUBJECT ENROLLMENT AND WITHDRAWAL**

### **11.1 Inclusion Criteria**

To be eligible for enrollment in this study, a subject must meet all of the following inclusion criteria:

1. AD, encompassing probable AD and MCI-AD based on 2011 NIA/AA criteria:
  - All cause dementia and probable AD (probable AD)  
In brief, subjects with probable AD dementia must have insidious onset,

worsening impairment in at least two cognitive areas (learning and recall, language, executive function, visuospatial skills), sufficient to significantly interfere with work or usual activities, that is not explained by delirium, drugs, major psychiatric disorder, medical illness, cerebrovascular disease, other forms of dementia, or neurological disorder. The accuracy of the diagnosis will be confirmed independently by the diagnosing physician at site.

OR

- MCI-AD

In subjects with MCI-AD, there should be evidence of concern about a change in cognition, in comparison with the person's previous level verified by a knowledgeable informant or clinician. Other mild cognitive deficits may also be present, but there must be preservation of independence in functional abilities. Subjects should not meet the criteria for dementia. The cognitive changes must be mild and there must be no evidence of a significant impairment in social or occupational functioning. Impairments must not be explained by delirium, drugs, major psychiatric disorder, medical illness, cerebrovascular disease, other forms of dementia, or neurological disorder.

2. Documented PET scan that is positive for amyloid; if most recent PET scan was performed >3 years prior to Screening and was negative, it may be repeated (a negative amyloid PET scan within the 3 years prior to Screening is exclusionary)
3. MMSE score of 16-27 (inclusive) at Screening, subject to stratification requirements
4. Global CDR score of 0.5 to 2 at Screening (if 0.5, including a score of >0 in one of the functional domains: Community Affairs, Home and Hobbies, or Personal Care)
5. Age <90 years at Screening
6. Females must meet one of the following:
  - Surgically sterile (hysterectomy, bilateral salpingectomy / oophorectomy) for at least 6 months minimum
  - Have undergone bilateral tubal occlusion / ligation at least 6 months prior
  - Post-menopausal for at least 1 year

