## 2.6. Randomization Methodology

With protocol version 5.0 (see Table 1), subjects who satisfied all eligibility criteria were randomized to one of three study regimens HMTM 16 mg/day, HMTM 8 mg/day, or control (4:1:4, at the study- rather than site-level). Randomization was stratified by (**bold** level will be used as reference category in statistical analyses, if needed and results are not population weighted):

Sponsor:	TauRx Therapeutics Ltd.		
Protocol:	TRx-237-039		
Document Version No.:	3.0	Document Date:	07-JUN-2023

---

- Severity (three levels: Mini-Mental State Examination (MMSE) **16-19 (moderate)**, 20-25 (mild), or 26-27 (MCI-AD)),
- Prior use of standard AD treatment (two levels: AChEI/memantine or **none**), and
- Region (two levels: North America or **Europe**).

Global enrollment across the whole study was managed such that subjects were assigned to the Screening MMSE severity groups with a target of approximately 2:3:1 (MMSE 16-19, MMSE 20-25, and MMSE 26-27, respectively) for those randomized under protocol version 5.0 and above. Each stratum was closed when the target enrollment was achieved.

If not indicated otherwise, any analysis or summary that groups subjects by prior use of AChEI and/or memantine, is inclusive of those with a prior history of such use and those who withdrew usage for the purposes of this study (such as lack of efficacy). When data are analyzed descriptively, discontinuation of AChEI and/or memantine before entering the study and discontinuation of AChEI and/or memantine for purposes of study participation (after entering the study) will be differentiated.

If a subject consented to protocol version 2.1 and did not reconsent to a later protocol version, the stratification information provided by the site is considered correct with respect to prior use of AChEI and/or memantine, unless there is specific information in the CRF that contradicts that. In earlier version of the protocol (v2.1), there was no stratum for MMSE as the inclusion criterion was to have an MMSE of 20-25; for all these subjects the stratum will be imputed as MMSE 20-25.

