##### 3.1.1. Double-Blind Populations

**Intention-to-Treat (ITT) Population:** all randomized subjects. Subjects are analyzed as randomized.

**Efficacy Modified Intention-to-Treat (E-MITT) Population:** all ITT subjects who received at least one dose of study drug and have a Baseline and at least one *valid* post-Baseline efficacy assessment (either ADAS-cog11 or ADCS-ADL23). Subjects are analyzed as randomized.

**MRI Imaging Modified Intention-to-Treat (MI-MITT) Population:** all ITT subjects who received at least one dose of study drug and have a Baseline and at least one *valid* post-Baseline volumetric MRI (either whole brain or temporoparietal lobe). Subjects are analyzed as randomized.

**PET Imaging Modified Intention-to-Treat (PI-MITT) Population:** all ITT subjects with screening CDR of 0.5 and who received at least one dose of study drug and have a Baseline and at least one *valid* post-Baseline SUVR assessment (temporal lobe). If data is available from subjects with a CDR > 0.5, these subjects will not be included in this population. Subjects are analyzed as randomized.

**Per Protocol (PP) Population:** all subjects who are in the E-MITT and MI-MITT population, without any important protocol deviation (see Section 3.2) that would deem the subject exclusionary from the PP Population (as per BDRM decision) or intercurrent medical events that could confound the interpretations. Subjects are analyzed as randomized. **Important here refers to a classification that is decided during BDRM based on the original protocol deviation classification as major/minor and their impact on key (efficacy/safety) outcomes of this study. The original classification as major/minor will be provided as well.**

A valid value means that the assessment was not affected by prior initiation of an AChEI and/or memantine.

**Safety Population:** all subjects who received at least one dose of study drug. Subjects are analyzed as treated. If a subject received different doses, the predominant treatment group (based on the number of doses) will be assigned.

**v5-Populations:** If the above-mentioned populations (ITT, E-MITT, MI-MITT, PI-MITT, PP, Safety) are restricted to subjects randomized under study protocol version 5.0 or higher, which are the primary efficacy analysis populations, the population names are: ITTv5, E-MITTv5, MI-MITTv5, PI-MITTv5, PPv5, and Safetyv5.

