#### 5.9.1.5. PET Estimand (ITTv5)

The PET Estimand is designed to answer the question on the treatment effect of HMTM dose of 16 mg/day as monotherapy versus control (containing a small amount of MTC) in the targeted population of subjects with *very mild* AD (CDR of 0.5) at Week 52, regardless of trial product discontinuation, based

Sponsor:	TauRx Therapeutics Ltd.		
Protocol:	TRx-237-039		
Document Version No.:	3.0	Document Date:	07-JUN-2023

on the  $^{18}\text{F}$ -FDG-PET temporal lobe in SUVR. If data is available from subjects with other than a CDR of 0.5, these will not be included in the analysis.

This estimand is constructed in line with ICH E9 (R1) addendum. The five components defining the estimand of interest are:

- A. Treatment:** 52 weeks HMTM dose of 16 mg/day or matching control (containing a small amount of MTC) as monotherapy, regardless of adherence.
- B. Population:** Subjects with very mild AD (CDR of 0.5) and as further described by the inclusion and exclusion criteria, randomized under protocol version 5.0 or higher.
- C. Patient-level outcome / variable:** Change from Baseline of the  $^{18}\text{F}$ -FDG-PET temporal lobe in SUVR at Week 52.
- D. Population-level summary:** Population weighted least squares means difference.
- E. Intercurrent Events:** Identification of ICE is as described for the primary estimand (see Section 5.9.1.1).  
**Events 1** will be handled according to a hypothetical strategy as if patients have stayed on treatment.  
In a sensitivity analysis all these subject withdrawals are assumed to be potentially treatment-related, which are then handled using the treatment policy approach from ICE #2.  
**Events 2** will be handled using a treatment policy approach assuming that the subjects withdrawing from treatment for treatment-related reasons do not retain any treatment effect after Baseline; the intervention effect / in this case is  $I=E*(1-w)$ , where  $E$  is the treatment effect at Week 52 and  $w$  is the fraction of subjects within the HMTM treatment group who withdraw for potentially treatment-related reasons up to Week 52.  
**Events 3** will be handled according to the original randomized treatment group assuming they did not start AChEI and/or memantine and will be analyzed the same as ICE #2.  

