## 7.2. Analysis Population

**Biomarker Population:** subjects randomized under protocol version 5.0 or higher, which completed the double-blind treatment phase, excluding the TOTOS (see Section 4.4). Subjects randomized under a protocol version before version 5 with available biomarker data at Week 52 and completed double-blind treatment phase will be included as well.

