### 7.3.2. Primary Outcomes

For each of the primary exploratory biomarkers P-tau181 and NfL, an ANCOVA will be used to analyze the change from Baseline at Week 52 visit within each treatment group (HMTM 16 mg/day, HMTM 8 mg/day, and control). In this ANCOVA, the change from Baseline at Week 52 will be compared pairwise

Sponsor:	TauRx Therapeutics Ltd.		
Protocol:	TRx-237-039		
Document Version No.:	3.0	Document Date:	07-JUN-2023

for these three treatment groups. The ANCOVA model will include the randomization stratification variables (see Section 2.6) as fixed factors, the respective efficacy Baseline value as covariate, and the treatment indicator; with the Kenward and Roger method used for calculating the denominator degrees of freedom for the tests of fixed effects. One table will present the LSM for the change from Baseline and the pairwise treatment contrasts at Week 52, and one table will present the p-values of the type 3 tests of the fixed effects along with the estimates of the factors and covariates which are included in the model.

In a sensitivity analysis, subject's age and sex, as well as *ApoE4* carrier status and plasma sample age will be added as further covariates in the primary model. The plasma sample age (of the Week 52 sample) is the difference between the day when the sample was analyzed and the day when the sample was taken + 1. For NfL: a mid-point sample analysis date will be applied, to calculate the plasma sample age. In a second and third sensitivity analysis, Baseline values of MRI whole brain volume and F-FDG-PET temporal lobe glucose uptake normalized to pons will be included separately as covariates as well. Factors with a p-value of 0.2 or smaller will be investigated further upon request.

In addition, this primary model will be repeated with the control group being restricted to the subpopulation with lowest parent MT.

This primary model will be repeated (not including the sensitivity analyses and not including the analysis with respect to the lowest parent MT control group) for the subgroups of the stratification variables region, prior use of AChEI and/or memantine, and Baseline MMSE severity (16-19, and 20-27). For the Baseline MMSE severity, the additional split into the subgroups of scores 16-21, and 22-27 will be done as well. This analysis will also be repeated for the verified AD diagnosis subgroups MCI-AD and probable AD.

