#### 7.3.5. Additional Analysis

The pairwise correlation of Baseline values between the primary exploratory biomarker (P-tau181 and NfL), and the above-mentioned scales and parameters (see Section 7.3.3) will be analyzed irrespective of the treatment group (not per treatment group).

For each of the primary exploratory biomarker (P-tau181 and NfL), an ANCOVA will be used to analyze the natural logarithm of percentage change from Baseline at Week 52. The ANCOVA model will be the same as for the primary outcome (see Section 7.3.2) and the two sensitivity analyses will be performed as well, one including subject's age and sex, as well as *ApoE4* carrier status and plasma sample age, and the second including MRI whole brain volume and  $^{18}\text{F}$ -FDG-PET temporal lobe glucose uptake. Additional analysis will be performed upon request.

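### The PET-adjusted biomarker sensitivity model runs only in subjects with a baseline FDG-PET scan, so a shift from the primary model mixes covariate adjustment with a change of population

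*SAP*

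**What the plan says.** SAP 7.3.2 defines the primary biomarker model as an ANCOVA of change from Baseline to Week 52 on treatment, the stratification factors and the baseline biomarker value. Three sensitivity models follow. The first adds age, sex, ApoE4 status and sample age. The second adds MRI whole brain volume. The third adds FDG-PET: "temporal lobe glucose uptake normalized to pons will be included separately as covariates as well". The sample code is PROC MIXED.

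SAP 7.3.5 repeats the ANCOVA for log percentage change with two sensitivity models, "the second including MRI whole brain volume and" FDG-PET temporal lobe uptake.

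The Protocol (Synopsis, Methodology) limits scanning: "Only subjects with a CDR 0.5 will undergo" FDG-PET. Eligibility in Protocol 11.1 is wider: "Global CDR score of 0.5 to 2 at Screening". SAP 7.2 sets no CDR limit on the Biomarker Population and also admits earlier enrolees: "Subjects randomized under a protocol version before version 5 with available biomarker data at Week 52 and completed double-blind treatment phase will be included".

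For the PET endpoint itself, SAP 3.1.1 gives an explicit rule: "If data is available from subjects with a CDR > 0.5, these subjects will not be included in this population". SAP 7.3.3 marks the PET correlations as restricted to baseline CDR 0.5. Neither 7.3.2 nor 7.3.5 carries such a note. SAP 4.5.2 confines multiple imputation to the two co-primary endpoints and MRI whole brain volume.

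**The concern.** A sensitivity analysis is informative when it changes one thing. The PET model changes two: it adds a covariate, and it removes every subject without a baseline scan. Missing scans follow disease severity by design, so the removed subjects are mostly the more impaired ones.

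Suppose the NfL contrast strengthens or fades once PET is added. A reader will take this as evidence about baseline metabolism, but the same movement could come from dropping most CDR 1 and 2 subjects. The SAP also says that factors with a p-value of 0.2 or smaller may be pursued on request. The PET p-value that could prompt this would come from the subset.

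In 7.3.5, joint entry would extend the problem to the MRI adjustment, which could otherwise use subjects of all severities.

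**Working it through.** The documents state neither the share of subjects at CDR 0.5 nor the number of baseline PET scans, so there is no plan figure to reproduce. The size has to be shown as a range.

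**Who enters each model**

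- Primary ANCOVA: Biomarker Population, any CDR (SAP 7.2, 7.3.2).
- PET model: the same, minus anyone without baseline PET. With no imputation (SAP 4.5.2), a record with a missing covariate cannot be used.
- Planned repeats of the primary model (SAP 7.3.2): region, prior AChEI or memantine use, MMSE 16-19 / 20-27, MMSE 16-21 / 22-27, MCI-AD / probable AD. None of these is the set of subjects with baseline PET.

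**Inputs for size**

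- MMSE target 2:3:1 for 16-19, 20-25 and 26-27 (SAP 2.6). Of 450 this is 150, 225 and 75.
- Assumed CDR 0.5 shares *a*, *b*, *c* in those three strata. The documents do not give them.
- 200 subjects per main arm, 50 on 8 mg/day, withdrawal 20% to 25% (SAP 5.3).

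**Formulas**

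- Share retained: s = (2a + 3b + c)/6. Loss = 1 − s.
- Standard error factor, with equal residual variance and equal loss across arms: 1/√s.
- Chance shift between the full-sample and subset contrasts when the true effect is the same in both groups and PET does nothing: √((1 − s)/s) full-sample standard errors. This follows because the full estimate is about s × (scanned) + (1 − s) × (unscanned).

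| a, b, c | Loss | SE factor | Chance shift (full-sample SEs) |
|---|---|---|---|
| 0.25, 1, 1 | 25.0% | 1.15 | 0.58 |
| 0.10, 1, 1 | 30.0% | 1.20 | 0.65 |
| 0, 1, 1 | 33.3% | 1.22 | 0.71 |
| 0, 0.75, 1 | 45.8% | 1.36 | 0.92 |
| 0, 0.5, 1 | 58.3% | 1.55 | 1.18 |
| 0, 0, 1 | 83.3% | 2.45 | 2.24 |

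Example, third row: s = (0 + 3 + 1)/6 = 0.667, so loss = 0.333, 1/√0.667 = 1.22 and √(0.333/0.667) = 0.71.

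**Subjects left.** After 20% to 25% withdrawal a main arm has 160 to 150 subjects and the 8 mg/day arm 40 to about 38. A one-third loss leaves about 107 to 100 and 27 to 25. An 83% loss leaves about 27 to 25 and 7 to 6.

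**Pre-version 5.0 subjects.** If about 50 (500 − 450) were all in the population and all had PET, the one-third case becomes 150/500 = 30%. This too is an assumption.

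**The case against.** The case on the other side has force on several points.

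- **Size.** A reader might infer from the MMSE target that at least a third of subjects are lost. The documents do not support this. MMSE and CDR are separate entry criteria, and nothing rules out CDR 0.5 in the MMSE 16-19 stratum. The loss could be below a third or far above it.
- **Who was scanned.** A reader might infer that the model contains only CDR 0.5 subjects. That is the rule from version 5.0. The Biomarker Population admits earlier enrolees, and SAP 3.1.1 and 5.9.3.2 foresee PET data outside CDR 0.5. They exclude such data from the PET endpoint, but 7.3.2 states no exclusion for the biomarker model.
- **COVID-19.** SAP 2.5 and Protocol 10.2.1 let the sponsor approve randomization without a baseline scan. This is a permission. Neither document says how often it was used, or that it was.
- **Other planned output.** The MMSE and diagnosis repeats show whether the treatment effect varies with severity, severity is a model factor, and the summary tables in SAP 7.3.1 will show n for PET. These help interpretation. They do not give the unadjusted contrast in the scanned subjects, and the last column of the table shows that the contrast can move by chance even without effect modification.
- **SAP 7.3.5.** It refers back to the 7.3.2 model, where MRI and PET enter separately, so joint entry is one reading and not a certainty.
- **Status.** SAP Section 7 is exploratory with nominal p-values.

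**Conclusion.** The point holds in a limited form. The PET-adjusted model for P-tau181 and NfL is a complete-case analysis in subjects with a baseline scan: mainly CDR 0.5, plus any earlier enrolees with PET. The primary model covers all severities. No planned output fits the unadjusted model in the scanned subjects, so a change in the contrast cannot be divided between adjustment and population.

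The size is not known from the documents. The 25% to 83% loss and the 1.15 to 2.45 standard error factor are scenarios, not bounds. They rest on assumed CDR mixes, on the version 5.0 enrolment target standing in for the Biomarker Population, and on unchanged residual variance, which PET adjustment or a more homogeneous subset could alter. The argument about interpretation does not need a particular fraction.

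A reader might infer that the biomarker results as a whole are affected. They are not: the primary ANCOVA and the other two sensitivity models in 7.3.2 do not use PET. Only the third model there is affected, together with the MRI-and-PET model in 7.3.5 if the two covariates enter jointly. This is a cheap improvement to an exploratory section.

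**What to change.** In SAP 7.3.2, fit the primary biomarker ANCOVA twice in the same subjects with baseline PET, once without and once with the PET covariate, and present the two side by side. State whether PET data at CDR above 0.5 are included, label the population accordingly, and report n by arm. The step from the primary model to the unadjusted subset model then shows the change of population, and the step from there to the PET model shows the adjustment.

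In SAP 7.3.5, say that MRI whole brain volume and FDG-PET enter separate models, as in 7.3.2, so that missing PET does not reduce the MRI adjustment. Give the PET model there the same paired presentation.

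The cost is one extra model per biomarker and outcome scale, a population label and a row of counts. No new data are needed.

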### 7.3.3. Secondary Outcomes

In the following, the changes from Baseline at Week 52 visit will be analyzed for the primary exploratory biomarkers P-tau181 and NfL through pairwise correlations.

These will be analyzed and presented through scatter plots with symbolized treatment group. For each treatment group, both the parametric Pearson correlation coefficient and the non-parametric Spearman's rank correlation coefficient and their corresponding p-values will be presented in this plot, along with the regression lines.

This analysis will be repeated for the Baseline MMSE score subgroups (16-19, 20-27, 16-21, 22-27), and the verified AD diagnosis subgroups MCI-AD and probable AD.

Furthermore, for each primary exploratory biomarker P-tau181 and NfL the change from Baseline at Week 52 visit will be compared pairwise with the change from Baseline at Week 52 for the following scales and parameters:

- ADAS-cog11 (after upscaling was applied)
- ADAS-cog13 (after upscaling was applied)
- ADCS-ADL23 (after upscaling was applied)
- MRI whole brain volume

Sponsor:	TauRx Therapeutics Ltd.		
Protocol:	TRx-237-039		
Document Version No.:	3.0	Document Date:	07-JUN-2023

- MRI lateral ventricular volume
- MRI temporoparietal lobe volume
- $^{18}\text{F}$ -FDG-PET temporal lobe glucose uptake (includes only subjects with a Baseline CDR of 0.5), normalized to pons and normalized to cerebellum

For each primary exploratory biomarker, the correlation between the change from Baseline at Week 52 visit with the predicted steady state plasma level of parent MT at Week 52 will be analyzed as well for the two HMTM treatment groups.

Sample SAS code (will be fully validated at the analysis stage):

```
PROC CORR DATA=dataset pearson spearman;  
  VAR endpoint1 endpoint2;  
  RUN;
```

#### 7.3.4. Additional Potential Biomarkers

Additional potential biomarkers are P-tau231, Core-proline tau, T-tau, and GFAP. For each of those biomarkers, if a decision will be made to investigate the respective potential biomarker further, the analyses described in the three previous sections (7.3.1 to 7.3.3) will be repeated. In addition to the pairwise comparison between P-tau181 and NfL, all other pairwise biomarker comparisons will need to be added.

